8.1.1 Part I: Single Ascending Dose (SAD)

In the SAD part of the study, single oral doses of GS-248 will be administered in 6 sequential cohorts, each of 8 subjects. Within each cohort, subjects will be randomised in a 3:1 ratio to receive either GS-248 (n=6) or placebo (n=2) in a blinded fashion. The proposed starting dose is 1 mg. The rationale for the starting dose and the planned dose escalation is detailed in

Section 8.3. Up to 2 additional dose cohorts can be explored based on the safety, tolerability and PK of the drug if recommended by the iSRC.

Subjects will come for 3 visits to the clinic. Screening (Visit 1) will take place from Day -28 to Day -1. For details on assessments, refer to Table 8.1-1. At Visit 2, subjects will be admitted to the clinic on Day -1 and will remain at the clinic until Day 3 for single dose IMP administration, safety, PK and PD (PD from cohort 3) assessments (Table 8.1-1 and Table 8.1-2). The subjects must fast for at least 10 h before the anticipated dosing time on Day 1. Water, but no other drinks, is allowed as desired except for 1 h before and 1 h after dosing. The first 2 subjects in each cohort will be dosed in a sentinel fashion; 1 subject will receive GS-248 and the other will receive placebo as randomised. The subjects will be carefully monitored by clinical staff during and after dosing. Vital signs and ECG will be checked at regular intervals as detailed in Table 8.1-2. There is immediate access to equipment, qualified staff and an ICU in case of an acute emergency. To give sufficient time for observation of any reactions, there will be at least 24 h before dosing of the third and fourth subject, who will be dosed on the same day approximately 2 h apart. The remaining 4 subjects will also be dosed 2 by 2, i.e. 2 subjects will be dosed on the same day approximately 2 h apart. A final end-of-study visit (Visit 3) will take place on Day 8 (± 2 days) or after early withdrawal.

In all cohorts, safety and PK will be assessed before and after dose as outlined in Table 8.1-1 and detailed in Table 8.1-2. Exploratory blood sampling for WBA and future biomarker analysis (from cohort 3 and onwards) and potential future metabolite analysis will be performed before and after dose (Table 8.1-1 and Table 8.1-2).

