| Blood sampling for future biomarker analyses ¹⁵ | | | X ¹⁵ | X ¹⁵ | | |
| Meals ¹⁶ | | X | X | X | X | |
| Baseline symptoms | X | X | | | | |
| AEs and SAEs | | | X ¹⁷ | | | |
| Prior and concomitant medications | X | | | | | |

1. Details in separate flow chart (Table 8.1-2). The duration of the residential period may be amended following review of data from earlier cohorts.
2. Screening and admission to the clinic may be conducted on the same day.
3. Confirmation of eligibility prior to randomisation. Day -1 or Day 1.
4. Weight only.
5. Random drug screening test may also be performed at the discretion of the investigator.
6. Screening: plasma/serum tests, other visits: urine test.
7. Short version of physical examination on Day 1.
8. Pre-dose assessments may be performed pre-dose Day 1 or on Day -1.
9. Clinical chemistry, haematology, coagulation, urinalysis (dip-stick), see Section 11.3.6.
10. Blood pressure and pulse, see Section 11.3.3.
11. For timing of assessments, refer to Table 8.1-2.
12. Ambulatory ECG telemetry for up to 24 h after IMP administration.
13. Administered under fasting conditions, i.e. fasting for 10 h before IMP administration until 4 h post administration.
14. Includes sampling for future exploratory analyses of potential GS-248 metabolites.
15. Sampling for WBA analysis and for future biomarker analyses starts at cohort 3. For timing of assessments, refer to Table 8.1-2.
16. Breakfast, lunch, snack, dinner and evening snack. Standardised meals during 24 h after dose. For timing of meals, refer to Table 8.1-2. No breakfast on Day 1. Breakfast only on Day 3.
17. From administration of IMP.

Table 8.1-2 Detailed schedule of events for Visit 2, Part I (SAD)

| Assessment/time-point | Day -1 | Day 1 | | | | | | | | | | | | | Day 2 | | Day 3 |
|---|----------------|------------------|---|-------|------|----|------|----|----|------------------|----|----|-----|-----|----------------|-----|----------------|
| | Admission | Pre-dose | 0 | 0.25h | 0.5h | 1h | 1.5h | 2h | 3h | 4h | 6h | 8h | 12h | 16h | 24h | 36h | 48 h |
| Inclusion/exclusion criteria | | X ¹ | | | | | | | | | | | | | | | |
| Pregnancy test (WOCBP) | X | | | | | | | | | | | | | | | | |
| Urine drug screen | X | | | | | | | | | | | | | | | | |
| Alcohol breath test | X | | | | | | | | | | | | | | | | |
| Physical examination | | X ^{1,2} | | | | | | | | | | | | | | | |
| Clinical laboratory profile | X | | | | | | | | | | | | | | | | X |

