Before initiating a new cohort, all subjects in the previous cohort must have been treated and safety, tolerability and PK data (at least 48 h data in Part I [SAD] and data up until and including 24 h post last dose in Part II [MAD]) for all treated subjects must have been evaluated by the iSRC.

If GS-248 is considered safe and tolerable, a written recommendation on the next dose level based on the predicted exposure will be provided to the Sponsor. Likewise, the iSRC will recommend dose levels for Part II and III, respectively, based on review of data from earlier cohorts/study parts.

Details regarding timing of iSRC review and the data to be reviewed will be provided in a separate iSRC charter. Based on emerging safety and PK information, the amount of safety and PK data to be reviewed after a completed cohort might be adjusted.

The voting members of the iSRC will consist of the Principal Investigator and the Sponsor's medically responsible person or delegate. In addition, the study clinical research manager (CRM), the study pharmacokineticist, additional Sponsor representatives and further internal or external experts will be invited and consulted as appropriate.

An adaptive dosing strategy will be applied to allow for a flexible and safe dose escalation. The planned dose escalation is outlined in Section 8.3.2 and Section 8.3.3. The actual doses given in each cohort will be guided by the iSRC recommendations based on available safety, tolerability and PK data. Every dose step is thus adjustable and the recommendation to the Sponsor may be to continue with a higher or lower dose than the intended dose, repeat the same dose level, continue with an intermediate dose level or to stop dosing.

The recommendation of the iSRC on the next dose level will be taken in consensus between the iSRC members and documented as appropriate. In case there is disagreement between the 2 voting members, the most conservative approach will be recommended. It is not acceptable to repeat a dose level where any of the dose escalation stopping rules have been met.

In Part I and Part II, 2 or 1 additional cohort(s), respectively, may be added as needed to test additional doses or dosing schemes, repeat the dose given in a previous cohort, to establish the target dose for Part III and subsequent studies and/or to reach steady state. In Part III, 1 additional cohort (10 patients) may be added.

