2 INTRODUCTION

This Statistical Analysis Plan (SAP) gives details regarding the statistical analyses for the comparison between treatment groups in the Part I (SAD), Part II (MAD) and Part IV of the study. Data presentation outlined in the final Clinical study protocol (CSP) for the study GS-1001. Any changes from the final CSP are given in Section 0.

A separate SAP have been constructed for each part of the study: GS-1001_SAP_v.1.0_11DEC2019 - SAD, GS-1001SAP_v.1.0_13FEB2020 - MAD and GS-1001_SAP_v.1.0_27FEB2020 - Part IV. Some of the analyses described in this SAP will supersede the analyses presented in each separate SAP, but for all TLF will the descriptive statistics tables be including both the Part II (MAD) and Part IV data using the FAS population. Data from the Part I (SAD) of the study will only be used in specific analyses of the exploratory endpoints (cohort number 3 to 6).

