3.4 Number of Subjects

The total number of subjects included in the study (Part I, Part II and Part IV) were 80.

- Part I (SAD): 48 subjects were randomised and dosed (6 cohorts, each of 8 subjects with 6 subjects receiving GS-248 (1mg, 5mg, 8mg, 40mg, 100mg and 300mg) and 2 receiving placebo).
- Part II (MAD): 24 subjects were randomised and dosed (3 cohorts, each of 8 subjects with 6 subjects receiving GS-248 (20mg, 60mg and 180mg) and 2 receiving placebo).
- Part III in the study was cancelled.
- Part IV (celecoxib): 8 subjects were randomised and dosed (1 cohort with 8 subjects receiving 200mg celecoxib BID).

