7.3 Tertiary/Exploratory Endpoint(s) Analysis

7.3.1.1 Analysis of mPGES-1 activity (PGE₂ levels) levels using whole blood assay

PGE₂ levels will be estimated for the absolute and percent change from pre-dose to both day 1 and day 10 subsequent timepoints. The change will be presented using summary statistics (one table per variable and comparison) and bar graphs (one graph per variable and comparison). The difference between all treatment groups, see table 3, will be analysed using Wilcoxon Rank Sum test and the p-values will be presented in a separate table (the Wilcoxon Rank sum test will only be applied for the changes between pre-dose and 24h value).

Table 3 – Comparison between treatment groups

Pairwise comparison groups	
Placebo	MAD 20mg
Placebo	MAD 60mg
Placebo	MAD 180mg
Placebo	Celecoxib
Celecoxib	MAD 20mg
Celecoxib	MAD 60mg
Celecoxib	MAD 180mg
MAD 20mg	MAD 60mg
MAD 20mg	MAD 180mg
MAD 60mg	MAD 180mg

STATISTICAL ANALYSIS PLAN

Protocol Version No: Final Version 2.0, 29MAY2019

Study Code: GS-1001

CTC Project No: 225-45.2018

CLINICAL TRIAL CONSULTANTS AB

A bar graph for the absolute and relative changes between pre-dose and Day 1 (24h) including treatment groups from SAD (cohorts 3 to 6 - 5mg, 40mg, 100, mg and 300mg), MAD (20mg, 60mg and 180mg), celecoxib 200 mg BID and Placebo, see table 4, including p-values in comparison to Placebo (using all placebo subjects in one group).

Table 4 – Comparison between treatment groups

Pairwise comparison groups	
Placebo	MAD 20mg
Placebo	MAD 60mg
Placebo	MAD 180mg
Placebo	Celecoxib
Placebo	SAD 5mg
Placebo	SAD 40mg
Placebo	SAD 100mg
Placebo	SAD 300mg
Celecoxib	MAD 20mg
Celecoxib	MAD 60mg
Celecoxib	MAD 180mg
Celecoxib	SAD 5mg
Celecoxib	SAD 40mg
Celecoxib	SAD 100mg
Celecoxib	SAD 300mg
MAD 20mg	MAD 60mg
MAD 20mg	MAD 180mg
MAD 20mg	SAD 5mg
MAD 20mg	SAD 40mg
MAD 20mg	SAD 100mg
MAD 20mg	SAD 300mg
MAD 60mg	MAD 180mg
MAD 60mg	SAD 5mg
MAD 60mg	SAD 40mg
MAD 60mg	SAD 100mg
MAD 60mg	SAD 300mg
SAD 5mg	SAD 40mg
SAD 5mg	SAD 100mg
SAD 5mg	SAD 300mg
SAD 40mg	SAD 100mg
SAD 40mg	SAD 300mg
SAD 100mg	SAD 300mg

A bar graph for Part I (SAD), cohorts 3 to 6 (5mg, 40mg, 100mg and 300mg), the within subject changes between pre-dose and Day 1 (24h) (both absolute and percent) with Wilcoxon test in comparison to placebo will be applied and presented in graphs.

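### SAP 3.4 and SAP 7.3.1.1 conflict, on their natural reading, about the dose given to SAD cohort 3, the first cohort with whole-blood PGE2 data

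*SAP*

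**What the plan says.** SAP 3.4 describes Part I as six cohorts of eight, with "6 subjects receiving GS-248 (1mg, 5mg, 8mg, 40mg, 100mg and 300mg) and 2 receiving placebo". It does not attach cohort numbers to the doses.

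SAP 2 restricts the SAD data in this combined plan: they "will only be used in specific analyses of the exploratory endpoints (cohort number 3 to 6"). SAP 7.3.1.1 then names the doses of those cohorts twice. The Day 1 comparison across parts is described as "including treatment groups from SAD (cohorts 3 to 6 - 5mg, 40mg, 100, mg and 300mg"), and the separate SAD display as "A bar graph for Part I (SAD), cohorts 3 to 6 (5mg, 40mg, 100mg and 300mg"). Table 4 lists SAD groups of 5, 40, 100 and 300 mg, and shell Table 14.4.1.1 has columns for the same four doses plus placebo. The 8 mg dose appears in SAP 3.4 and nowhere else.

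The protocol fixes which cohorts have these data. Table 8.1-1, footnote 15, says: "Sampling for WBA analysis and for future biomarker analyses starts at cohort 3". Protocol 8.1.1 says that "single oral doses of GS-248 will be administered in 6 sequential cohorts, each of 8 subjects". SAP 8, which lists the changes from the protocol, does not mention cohort order or the dose of cohort 3.

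**The concern.** Part I is an ascending-dose part run in sequential cohorts, so a reader takes a rising list of six doses for six cohorts to be in cohort order. The start of the list supports this: the tentative schedule in Protocol Table 8.3-2 puts 1 mg in cohort 1 and 5 mg in cohort 2, and SAP 3.4 also begins with 1 and 5. On that reading cohort 3 received 8 mg, while the PD section calls it 5 mg.

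The disputed group matters more than its size suggests. Whichever label is right, it is the lowest GS-248 dose with whole-blood data, because the next dose up in the Day 1 comparison is MAD 20 mg. The whole-blood assay is also the one exploratory endpoint that Protocol 7.3.1 commits to the clinical study report. A wrong label would misstate the dose at which the smallest tested exposure did or did not change PGE2.

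**Working it through.** No sample-size or test formula applies. The check sets the two dose lists side by side, asks which cohort orders could satisfy both, and counts the outputs that carry the label.

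**1. Subject total.** The counts in SAP 3.4 agree with each other: 6 × 8 + 3 × 8 + 8 = 48 + 24 + 8 = 80, the stated total. The conflict concerns doses, not numbers of subjects.

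**2. Side by side.**

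| SAD cohort | SAP 3.4, in list order | SAP 7.3.1.1 | Whole-blood sampling planned |
|---|---|---|---|
| 1 | 1 mg | not named | no |
| 2 | 5 mg | not named | no |
| 3 | 8 mg | 5 mg | yes |
| 4 | 40 mg | 40 mg | yes |
| 5 | 100 mg | 100 mg | yes |
| 6 | 300 mg | 300 mg | yes |

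One of the four PD cohorts differs. If the 3.4 order is the cohort order, the group labelled 5 mg holds the 8 mg subjects, and the label is off by a factor of 8 / 5 = 1.6.

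**3. Can both lists be true?** Six doses have 6! = 720 possible orders. Fixing cohorts 3 to 6 as 5, 40, 100 and 300 mg leaves only 1 and 8 mg for cohorts 1 and 2, which gives two orders: 1-8-5-40-100-300 and 8-1-5-40-100-300. Neither rises throughout. Only the first begins at the protocol's proposed 1 mg.

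Dose ratios between successive cohorts:

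- List order 1-5-8-40-100-300: 5, 1.6, 5, 2.5, 3.
- Order 1-8-5-40-100-300: 8, 0.625, 8, 2.5, 3.

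Protocol 8.3.2 allows steps of up to 8-fold when exposure after the first cohort is appreciably below prediction or not quantifiable. It also allows de-escalation for limiting safety or tolerability. Protocol 8.3.8 lets the safety committee recommend that the study "continue with a higher or lower dose than the intended dose". The second order is therefore possible under the protocol, though neither document says that it happened.

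**4. Outputs that carry the label.** In Table 4, SAD 5 mg is paired with placebo, celecoxib, MAD 20, MAD 60, SAD 40, SAD 100 and SAD 300 mg: 7 of 32 contrasts. Nine groups would give 9 × 8 / 2 = 36 pairs. Table 4 omits the four between MAD 180 mg and the SAD groups, so the count here is 7 and not 8. The label also heads one of the four active columns of Table 14.4.1.1 and appears in Figures 14.4.2.x and 14.4.3.x.

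**The case against.** A reader might infer that one PD group must be mislabelled or have no data, and that the two SAP sections cannot both stand. The documents do not support that. SAP 3.4 is a subject-count section, does not number the cohorts, and may simply be sorted by dose. If cohort 2 received 8 mg and cohort 3 received 5 mg, both lists are true, the PD label is correct and the samples exist. The absence of 8 mg from the PD outputs would then be expected, because cohort 2 was not sampled for the assay.

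Other points on this side are fair. The 5 mg label is used consistently in both sentences of 7.3.1.1, in Table 4 and in the shell, while 8 mg occurs once; an error, if there is one, may lie in 3.4. The separate SAD SAP, which SAP 9 lists as delivered and does not mark as superseded, may contain a cohort-to-dose map. The endpoint is exploratory, with no stated hypotheses and no multiplicity adjustment, and no dose-response model is planned that the lowest dose could distort. The fear that selecting subjects by dose would return an empty column is conjecture: the SAP already names the groups by cohort number as well as dose, Protocol 9.2 puts the cohort in the second digit of the randomisation number, and an empty column would be noticed.

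These points remove any claim that an error is proven, and they lower the severity. They do not remove the ambiguity. This SAP is the one from which the combined PGE2 outputs will be produced, and from it alone a reader cannot tell what cohort 3 received. A wrong label, unlike an empty column, would not show on output review.

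**Conclusion.** The concern holds as an unresolved conflict and not as a demonstrated mislabelling. In list order, SAP 3.4 gives cohort 3 a dose of 8 mg; SAP 7.3.1.1 and its outputs give 5 mg. Either the PD label is wrong, or 3.4 is not in cohort order and the label is right. The documents do not decide between these, and this review does not say which dose is right.

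The extent is one of four SAD PD groups (6 active subjects), 7 of 32 contrasts, one table column and the Day 1 graphs. The 1.6-fold label error arises only under the first reading, which assumes that 3.4 is in cohort order. Safety and PK analyses are specified in the earlier SAPs and are not touched by this point. Because the effect is confined to the exploratory PGE2 readout, the severity is should-fix.

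**What to change.** Before the PGE2 outputs are run:

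- Check the dose given to each SAD cohort against the dosing and randomisation records, and reconcile the two SAP sections.
- State one explicit cohort-to-dose map in SAP 3.4, with cohort numbers. If the doses did not rise in cohort order, say so there.
- Carry that map unchanged into SAP 7.3.1.1, Table 4, Table 14.4.1.1 (and the p-values in Table 14.4.1.2) and Figures 14.4.2.x and 14.4.3.x.
- Select the SAD PD groups by cohort number, using the randomisation number, and attach the dose afterwards as a label.

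The cost is one check of existing Part I records and edits to SAP wording and shell headings. No new data and no change of method are needed.

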7.3.1.2 AA metabolites in urine

The AA metabolites that will be analysed in urine are PGEM, PGIM and TXM. The AA metabolite concentration will be normalised by urine creatinine concentration and total excretion over 24 hours will be calculated:

- Actual concentration data
- Values normalised by urine creatinine concentration
 - Formula : $ng/mg = \frac{AA\ metabolite\ (ng/mL) * 1000}{U-creatinine\ (mmol/L) * 113\ (g/mol)}$
- Calculated total excretion over 24 h (described in previous SAP as Normalised values for urine volume)
 - Formula: $ng = AA\ metabolite\ (ng/mL) * urine\ volume\ (ml)$

Each metabolite will be estimated for the absolute and percent change from pre-dose to post-dose. The changes will be presented using summary statistics (one table per variable and comparison) and bar graphs (one graph per variable and comparison). The difference between all treatment groups, see table 3, will be analysed using Wilcoxon Rank Sum test and tabulated.

7.3.1.3 ADMA, L-Arginine

ADMA/L-arginine and L-arginine will be estimated for the absolute and percent change from pre-dose to 2h, 8h and 24h. The change will be presented using summary statistics (one table per variable and comparison) and bar graphs (one graph per variable and comparison). The difference between all treatment groups, see table 3, will be analysed using Wilcoxon Rank Sum test and will be presented in a table.

7.3.1.4 Renal creatinine clearance 24 h (ClCr):

Formula:

- AeCreatinine (mmol/24h) = Total sum over 24 hours of U-Creatinine (mmol/L) * U-Volume (L), as calculated for each urine fraction and summarized.
 - ClCr (L/h) = AeCreatinine (mmol)*1000 / [24 (h)*P-Creatinine (umol/L)]
 - ClCr (mL/min) = ClCr (L/h) * 1000/60

P-creatinine at day -1 and day 9 will be used for the MAD cohorts in the calculations, for the celecoxib cohort will screening and follow-up values be used.

Renal creatinine clearance will be presented in a table including Wilcoxon rank sum test p-value for the comparison between all the treatment groups.

STATISTICAL ANALYSIS PLAN

Protocol Version No: Final Version 2.0, 29MAY2019

Study Code: GS-1001

CTC Project No: 225-45.2018

CLINICAL TRIAL CONSULTANTS AB

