17. Standardised lunch, snack, dinner and evening snack at approximately 4, 7 and 9 and 11 h post breakfast. Breakfast only on Day 3 and Day 12.
18. Standardised lunch at least 4 h post-dose.

8.1.4 **Part IV: Celecoxib – open cohort with healthy volunteers**

In Part IV of the study, 200 mg celecoxib will be administered to 8 healthy volunteers twice daily for 10 days (i.e. 400 mg/day for 10 days).

Subjects will come for 5 visits to the clinic. Screening (Visit 1) will take place from Day -28 to Day -2. For details on assessments, refer to Table 8.1-7. At Visit 2, subjects will be admitted to the clinic in the morning of Day -1 for pre-dose assessments including a 24 h baseline urine collection and will remain at the clinic until Day 2 for IMP administration and PD assessments (Table 8.1-7). Subjects will be discharged from the clinic after the morning dose on Day 2.

From the evening of Day 2 to the evening of Day 8, subjects will self-administer celecoxib at home twice daily (morning and evening) and register each administration in an electronic diary (ViedocMe). Any reactions or use of concomitant medication will also be registered in ViedocMe. On Day 5 (Visit 3), the subjects will be contacted by phone for a drug accountability and AE check-up.

Subjects will again be residential at the clinic between Day 9 and Day 11 (Visit 4) for IMP administration and exploratory PD assessments. The last dosing day is Day 10. Urine collection for exploratory PD analysis will be performed during 24 h after the last morning dose on Day 10. A final end-of-study visit (Visit 5) will take place on Day 19 (± 2 days) or after early withdrawal.

Each subject is expected to participate in the study for approximately 47 days including a 27-day screening period.

The schedule of events for Part IV is shown in Table 8.1-7.

Study assessments are described in Section 11.

Safety assessments include: AE reporting and use of concomitant medications, see Section 11.3.

Exploratory assessments include: blood sampling for analysis of mPGES-1 activity (PGE₂ levels) in an *ex vivo* WBA, blood and urine sampling for analysis of ADMA in plasma and AA metabolites in urine, and blood and urine sampling for future exploratory biomarker analysis, see Section 11.5.

Table 8.1-7 Part IV Schedule of events, celecoxib

| Visit | Screening | Residential | | | At home | Telephone call | At home | Residential | | | End-of-study |

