8. Urine for PD analysis will be collected at the following intervals: 0 to 6 h, 6 to 12 h and 12-24 h post administration of celecoxib on Day 1 and Day 10. In addition, baseline urine is collected -24 h to -12 h and -12 h to 0 h prior to the first celecoxib administration on Day -1/Day 1.
9. Breakfast, lunch, snack, dinner and evening snack. Breakfast only on Day 2 and 11.
10. From administration of IMP.

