Figure 14.6.3.x. ADMA/L-Arg and L-Arg levels Day 1 and Day 10 MAD cohorts and Celecoxib ([analysis set])

Bar graph with p values presenting absolute and relative change from baseline for MAD cohorts and Celecoxib. Graphs presented by dose group and all timepoints (one graph per dose group).

STATISTICAL ANALYSIS PLAN

Protocol Version No: Final Version 2.0, 29MAY2019

CTC Project No: 225-45.2018

CLINICAL TRIAL CONSULTANTS AB Study Code: GS-1001

Table 14.7.1.1. Renal creatinine clearance ClCr ([analysis set])

Assessment (unit)	Result Category	Assessment timepoint	GS-248 20 mg	GS-248 60 mg	GS-248 180 mg	PLACEBO	Celecoxib	
[Parameter 1] (unit)	Measured value	[Assessment timepoint 1]	n	x	x	x	x	x
		Mean (SD)	x.xxx (x.xxx)	x.xxx (x.xxx)	x.xxx (x.xxx)	x.xxx (x.xxx)	x.xxx (x.xxx)	
		Median (Min, Max)	x.xxx (x.xx, x.xx)	x.xxx (x.xx, x.xx)	x.xxx (x.xx, x.xx)	x.xxx (x.xx, x.xx)	x.xxx (x.xx, x.xx)	
		[Assessment timepoint 2]	n	x	x	x	x	x
		Mean (SD)	x.xxx (x.xxx)	x.xxx (x.xxx)	x.xxx (x.xxx)	x.xxx (x.xxx)	x.xxx (x.xxx)	
		Median (Min, Max)	x.xxx (x.xx, x.xx)	x.xxx (x.xx, x.xx)	x.xxx (x.xx, x.xx)	x.xxx (x.xx, x.xx)	x.xxx (x.xx, x.xx)	
	Absolute change from baseline	[Assessment timepoint 2]	n	x	x	x	x	x
		Mean (SD)	x.xxx (x.xxx)	x.xxx (x.xxx)	x.xxx (x.xxx)	x.xxx (x.xxx)	x.xxx (x.xxx)	
		Median (Min, Max)	x.xxx (x.xx, x.xx)	x.xxx (x.xx, x.xx)	x.xxx (x.xx, x.xx)	x.xxx (x.xx, x.xx)	x.xxx (x.xx, x.xx)	
		Wilcoxon between groups p-value	x.xxxx	x.xxxx	x.xxxx		x.xxxx	
	Relative change from baseline (%)	[Assessment timepoint 2]	n	x	x	x	x	x
		Mean (SD)	x.x (x.x)	x.xxx (x.xxx)	x.xxx (x.xxx)	x.xxx (x.xxx)	x.xxx (x.xxx)	
		Median (Min, Max)	x.x (x, x)	x.xxx (x.xx, x.xx)	x.xxx (x.xx, x.xx)	x.xxx (x.xx, x.xx)	x.xxx (x.xx, x.xx)	
		Wilcoxon between groups p-value	x.xxxx	x.xxxx	x.xxxx		x.xxxx	

Data based on [ANALYSIS SET]. All p-values in comparison to PLACEBO.

[STUDYID] [DOMAIN]: [PARAMETER CATEGORY], SAS program: descriptive_stat_tables.sas. Run by: [USERNAME], [USER EMAIL] [TIMESTAMP]

STATISTICAL ANALYSIS PLAN

Protocol Version No: Final Version 2.0, 29MAY2019

CTC Project No: 225-45.2018

CLINICAL TRIAL CONSULTANTS AB Study Code: GS-1001

Table 14.7.1.2. P-values for pairwise comparisons between all dose groups for Renal creatinine clearance ClCr

STATISTICAL ANALYSIS PLAN

Protocol Version No: Final Version 2.0, 29MAY2019

CTC Project No: 225-45.2018

CLINICAL TRIAL CONSULTANTS AB Study Code: GS-1001

Listings

STATISTICAL ANALYSIS PLAN

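### Celecoxib creatinine clearance uses screening and off-treatment follow-up plasma, MAD uses Day -1 and on-treatment Day 9, and the resulting changes are tested against each other with no caveat

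*SAP*

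**What the plan says.** SAP Section 7.3.1.4 defines ClCr as 24 h urinary creatinine excretion divided by 24 h times plasma creatinine, and sets two plasma rules in one sentence. For Part II, "P-creatinine at day -1 and day 9 will be used for the MAD cohorts in the calculations"; for Part IV, "for the celecoxib cohort will screening and follow-up values be used". The same section then asks for a "Wilcoxon rank sum test p-value for the comparison between all the treatment groups". The Table 14.7.1.1 shell places those p-values under both absolute and relative change from baseline, with a celecoxib column. Table 14.7.1.2 is titled "P-values for pairwise comparisons between all dose groups for Renal creatinine clearance ClCr". Neither shell has a footnote on plasma timing.

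Protocol Section 8.1.4 gives the Part IV timing. For the baseline plasma: "Screening (Visit 1) will take place from Day -28 to Day -2. For details on assessments, refer to Table 8.1-7". For the end plasma: "A final end-of-study visit (Visit 5) will take place on Day 19 (± 2 days) or after early withdrawal". The last dosing day is Day 10. Protocol Table 8.1-7 marks the clinical laboratory profile only at these two visits. Urine follows a different timetable. At the end of treatment, "Urine collection for exploratory PD analysis will be performed during 24 h after the last morning dose on Day 10"; before treatment, "baseline urine is collected -24 h to -12 h and -12 h to 0 h prior to the first celecoxib administration" (Table 8.1-7, footnote 8). Urine is also collected over 24 h on Day 1.

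**The concern.** ClCr is inversely proportional to plasma creatinine, so the day of the plasma sample matters as much as the day of the urine collection. In the MAD groups the end-of-treatment plasma comes from a dosing day. In the celecoxib group it comes from a visit at least a week after dosing stopped, while the matching urine was collected on treatment. If a drug changes plasma creatinine and the change reverses after dosing, the GS-248 columns will show it and the celecoxib column will show it only in part or not at all.

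Two wrong readings could follow. A real celecoxib effect could be missed against placebo, or GS-248 could look worse than celecoxib when the two act alike; if the effect were a rise in clearance, the distortion would run the other way. The protocol names an exploratory comparison of PD effects between celecoxib and GS-248 as a purpose of the study, so a reader may well use this column. Nothing in the tables says it was built differently.

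**Working it through.** **Inputs.** Plasma days: SAP 7.3.1.4. Visit windows, dosing days and urine intervals: Protocol 8.1.2, 8.1.4, Tables 8.1-3 and 8.1-7. Group sizes: SAP 3.4 (8 celecoxib, 6 per GS-248 dose, 3 × 2 = 6 MAD placebo). The documents give no ClCr effect, variability or power figure, so there is nothing of the plan's own to reproduce.

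**Timing** (there is no Day 0). SAP 7.3.1.4 names no urine interval. I infer that baseline pairs with the pre-dose urine and the end value with the Day 10 urine.

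| | MAD and placebo | Celecoxib |
|---|---|---|
| Baseline plasma before Day -1 | 0 days | 1 to 27 days (Day -2 to Day -28) |
| End plasma relative to Day 10 | 1 day before | 7 to 11 days after (Day 17 to Day 21) |
| Interval between the two plasma samples | 9 days | 18 to 48 days |

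**Comparisons affected.** Five groups give 5 × 4 / 2 = 10 pairs, of which 4 include celecoxib (against placebo and 20, 60 and 180 mg). If both scales in Table 14.7.1.1 are tested for each pair, that is 8 of 20 p-values per post-dose time point.

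**Attenuation.** Let *e* be the true on-treatment change in clearance and *r* the fraction of the plasma change that has recovered by follow-up. With urinary creatinine excretion unchanged, on-treatment plasma is 1/(1+*e*) times baseline, and follow-up plasma is 1 + (1−*r*)(1/(1+*e*) − 1) times baseline. The expected celecoxib estimate is therefore

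1 / [1 + (1−*r*)(1/(1+*e*) − 1)] − 1.

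Example: *e* = −10%, *r* = 0.5 gives 1/(1 + 0.5 × 0.1111) − 1 = −5.3%.

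| True change | No recovery | Half | Full |
|---|---|---|---|
| −5% | −5.0% | −2.6% | 0% |
| −10% | −10.0% | −5.3% | 0% |
| −20% | −20.0% | −11.1% | 0% |
| +10% | +10.0% | +4.8% | 0% |

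**False differences.** Suppose GS-248 (n = 6) and celecoxib (n = 8) have the same true effect and are compared by an exact two-sided Wilcoxon test at 5%. The attainable size for 6 against 8 is 0.0426. I simulated 40,000 trials per cell, assuming a plasma CV of 4% and a urine CV of 5% to 25% per measurement. The range in each cell runs over the urine CVs; the top figure is at 5%.

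| True fall in both groups | No recovery | Half | Full |
|---|---|---|---|
| 5% | 4% | 4–6% | 5–14% |
| 10% | 4% | 5–14% | 7–45% |
| 20% | 4% | 7–46% | 17–98% |

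**Missed effect.** If only celecoxib lowers clearance, by 10%, the chance of detecting it against placebo with no plasma recovery is 7–45% over the same urine CVs. With full recovery it is 4%, the size of the test.

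**Baseline gap alone.** Treating it as extra random variation (screening plasma CV 4–12%, no drug effect) leaves the rate at 4%. The follow-up plasma is the source of the problem.

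**The case against.** The SAP used the only plasma creatinine scheduled for Part IV, and it states both sources openly in Section 7.3.1.4. The screening value also meets the SAP 4.3 definition of baseline, the latest measurement before first dose. ClCr supports no listed objective or endpoint, and the SAP states no hypotheses and requires significant findings to be reviewed for medical relevance. Part IV is open and non-randomised, so celecoxib contrasts would be weak even with perfect timing. The bias is conditional, and the largest error rates need an assumed 20% fall, full recovery and low urine variability. For falls of up to 10% and a urine CV of 15% or more, the rate stays at or below 11%. The table shells are unfilled, and a footnote is easily added.

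Most of this stands, and it limits the severity. It does not justify the p-values. Having no comparable sample is a reason to describe the celecoxib values, not to test them. Meeting the baseline definition does not align the groups and does nothing for the end value. Review for medical relevance covers only significant results, so it would not catch a celecoxib effect that the off-treatment plasma had removed.

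**Conclusion.** The concern holds. The two plasma rules, the visit windows and the all-group testing are explicit in the documents. As specified, 4 of the 10 ClCr comparisons do not compare on-treatment change like for like; the other 6 are sound on this point.

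Two elements are inferred: the pairing of urine with plasma, and the testing of change from baseline, which comes from the table shell and not from the text of 7.3.1.4. The size of the bias cannot be known from the documents. It ranges from none (no effect, or no recovery by Day 17 to 21) to complete loss of the celecoxib effect (full recovery). The error rates above are illustrations resting on assumed effects, recovery and CVs. The harm is a misleading comparator column in an exploratory analysis, and no primary or secondary result changes. The plan should be corrected, but this is not a critical flaw.

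**What to change.** In SAP 7.3.1.4 and Tables 14.7.1.1 and 14.7.1.2:

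- Remove the Wilcoxon p-values for the celecoxib ClCr change and keep those among GS-248 doses and placebo.
- Omit the celecoxib change, or show it descriptively with a footnote giving both timing differences: screening plasma at baseline, and off-treatment Day 19 ± 2 plasma at the end.
- State which urine interval is paired with which plasma sample.
- List ClCr in SAP Section 8 as an added analysis. That section lists L-arginine but not ClCr, and the protocol collects urine creatinine only to normalise the PD urine results (Tables 11.3-1 and 11.3-2, footnotes).

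This costs wording and shell edits, plus the loss of an exploratory contrast that is not valid as specified.

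Two extras are optional. A labelled sensitivity analysis could apply the screening and Day 19 plasma rule to all five groups, since Protocol Table 8.1-3 schedules MAD chemistry at both visits. It aligns timing but does not measure an on-treatment change, and it restores the nominal 4% only if plasma recovers equally under both drugs. With a 20% fall, half recovery on GS-248 and full recovery on celecoxib, the simulated false-difference rate is 8–55%. Alternatively, creatinine could be assayed in stored Part IV Day 1 pre-dose and Day 10/11 plasma, if it was kept (Protocol 12.3 permits retention but does not require it) and the assay is comparable with the hospital laboratory's.
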